6 BASELINE, EFFICACY AND SAFETY EVALUATIONS

6.1 Schedule of Evaluations

The following table summarizes the data to be collected for each patient over the course of his/her participation in the TRACE study.

Table 2 Event schedule

	Initial Collection of Data	Cryoablation Data	Subsequent Visit(s) Based Upon Site Standard of Care
Enrollment Date	X		
Informed Consent Obtained	X		
Demography	X		
Comorbidities	X		
Medical History	X		
Concomitant Medications	X		X
Imaging (Baseline)	X		
Quality of Life (SF-12)	X		X (6 & 12 mo)
Pre-Cryo Biopsy	X (if available)		
Pre-Cryo Pathology	X (if available)		
Intra-operative Biopsy		X (if available)	
Intra-operative Pathology		X (if available)	
Cryotherapy Procedure		X	
Intra-operative Complications		X	
Hospital Stay		X	X
Clinical Laboratories	X	X (if available)	X
Post-operative Complications		X	X
Post-operative Interventional Treatment		X	X
Follow-Up			X
Imaging Follow-up			X
Biopsy Follow-up			X (if available)
Pathology Follow-up			X (if available)
Primary Lesion Recurrence			X
New Renal Lesion Emergence			X
Emergence of new neoplastic disease (any type)			X
Development of metastatic disease			X
Withdrawal			X

6.2 Time Point Algorithms

6.2.1 Relative Days

Relative days will be calculated for both efficacy and safety endpoints. The date of cryoprocedure will be considered relative day 1, and the day before the cryoprocedure will be relative day -1. Patients could also have received subsequent cryoprocedures, and these are recorded in the eCRF page named “Follow-up/Further Cancer Therapy” and not on an additional eCRF page named “Cryotherapy Procedure.” For the purposes of this SAP, date of cryoprocedure refers to the date of the first cryoprocedure. Relative days will be calculated as follows only when the full assessment date is known (i.e., partial dates will have missing relative days):

For days on or after cryoprocedure:

Date of assessment – Date of cryoprocedure + 1

For days before cryoprocedure:

Date of assessment – Date of cryoprocedure

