8.6 Analysis of Efficacy Parameters

8.6.3 *Change in lesion size*

Change from baseline and percentage change from baseline in lesion size will be summarized with descriptive statistics for each follow-up visit. This will be done separately for greatest trans-axial diameter and for lesion volume. A per-lesion and a per-patient analysis of change in lesion size will be provided.

Waterfall plots of the percentage change in the lesion size, as measured by greatest trans-axial diameter, will be given for each follow-up visit.

8.6.4 *Post-cryoablation lesion recurrence with enhancement and lesion progression with enhancement*

The number and percentage of patients with post-cryoablation lesion recurrence with enhancement, and the number and percentage of patients with post-cryoablation lesion progression with enhancement, (as defined in Section 6.4.2) will be given for each follow-up visit. The percentage will be based on the number of patients who remain in follow-up at that visit (i.e. excluding patients who have withdrawn, died or completed after the end date of the analysis window). For example, if a patient withdrew from the study or died within the 36 month analysis visit window, the patient would be included in the 36 month visit percentage calculation, but would not be included in the percentage calculations for subsequent visits.

This analysis will also be performed for the following subgroups:

- NS complexity categories at baseline
- Procedure method
- Lesion size at baseline, by greatest trans-axial diameter, as categories of ≤ 4 cm and > 4 cm
- Comorbidities (human immunodeficiency virus [HIV]/immunocompromised; diabetes; hypertension; obesity; blood clotting disorder; abdominal surgery; cardiovascular; retroperitoneal surgery; von Hippel-Lindau; cancer, other than renal)
- Patients who did and did not receive subsequent cryoablation (note: these patients will need to be identified manually from the response to the ‘Specify type of local or systemic therapy’ field on the ‘Follow-up/Further cancer therapy’ eCRF page)
- Area suspicious for lesion recurrence (yes, no) (as defined in Section 6.4.1) at the same post-cryoablation visit
- Baseline lesion classification (i.e., exophytic, mesophytic, endophytic)

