8.6.9 Additional efficacy assessments

8.6.9.1 Lesion status

Lesion status (i.e., responses to the question “What is the status of the lesion?” in the follow-up lesion assessment eCRF page), will be summarized separately for each follow-up visit, as count and percentage in a per-lesion analysis. The number and percentage of lesions for each category will be given, together with a 95% CI based on Wilson (1927).

This analysis will also be performed separately

- For patients with <3 freeze cycles and <3 thaw cycles
- By procedure method (laparoscopic and percutaneous)
- By procedure method (laparoscopic and percutaneous) in patients with <3 freeze cycles and <3 thaw cycles
- By needle type (Needles with the cautery feature [IceRod CX, IceFORCE 2.1 CX, and IcePearl 2.1 CX] vs other types)

The following baseline results will be provided for lesions with a status of ‘No longer present’ at any follow-up visit:

- Number and percentage of lesions that are cystic or solid at baseline
- Baseline lesion size, by greatest trans-axial diameter, will be summarized with descriptive statistics and also as categories of ≤ 4 cm and > 4 cm
- Number and percentage in each frozen section pathology result category at baseline
- Number and percentage in each permanent section pathology result category at baseline

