8.8.2 New therapies for renal cancer

The analyses described in this section will be performed on the ITT and RCC populations, separately for each visit.

The following will be summarized by the number and percentage of patients:

- Disease free status
- Patients who received a new therapy for renal cancer
- Patients who received local and systemic therapy

- Patients who received subsequent cryoablation (note: these patients will need to be identified manually from the response to the ‘Specify type of local or systemic therapy’ field on the ‘Follow-up/Further cancer therapy’ eCRF page)

Duration (months) between date of cryoprocedure and date of new local therapy will be summarized with descriptive statistics. Also, the duration (months) between dates of first and subsequent cryooperations (retreatments) will be summarized.

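### The by-visit lesion tables have no rule for assessments made after repeat ablation or other kidney-cancer therapy, so rescued lesions can appear unlabelled as successes of the first procedure

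*SAP*

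**What the plan says.** SAP 6.2.1 anticipates retreatment: "Patients could also have received subsequent cryoprocedures, and these are recorded in the eCRF page named" Follow-up/Further Cancer Therapy, with no second procedure page. It then fixes the origin: "For the purposes of this SAP, date of cryoprocedure refers to the date of the first cryoprocedure". The windows in SAP 6.2.2 run from that day to beyond month 60.

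Three sets of lesion results are tabulated on this clock:

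- **Lesion size (SAP 8.6.3):** "Change from baseline and percentage change from baseline in lesion size will be summarized with descriptive statistics for each follow-up visit", with a waterfall plot of diameter change at each visit.
- **Recurrence and progression with enhancement (SAP 8.6.4):** "The percentage will be based on the number of patients who remain in follow-up at that visit". Only patients who withdrew, died or completed leave the denominator.
- **Lesion status (SAP 8.6.9.1):** results "will be summarized separately for each follow-up visit, as count and percentage in a per-lesion analysis". The listed splits are freeze/thaw cycles, procedure method and needle type. Baseline features are also profiled for lesions recorded as *No longer present* at any follow-up visit.

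Retreatment appears in two places. SAP 8.6.4 repeats its table for "Patients who did and did not receive subsequent cryoablation", identified by hand. SAP 8.8.2 counts, at each visit, "Patients who received a new therapy for renal cancer" and those re-ablated, and summarises the intervals to new local therapy and to retreatment.

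For TTR, SAP 6.4.4 requires a lesion status of *Recurrent* together with contrast enhancement. SAP 5.2 records that progression no longer counts as an event. The three censoring rules in SAP 8.6.6.1 concern a missing baseline assessment, two or more missed visits before recurrence, and absence of recurrence. None mentions new therapy.

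**The concern.** A lesion that fails, is re-ablated or removed, and then looks controlled enters the month-24 to month-60 tables like a lesion controlled by the first ablation. A reader of those tables would take them as evidence of how long the first procedure lasts. Wherever rescue works, the error favours the device. The same mixing reaches the *No longer present* profile, which would describe lesions eliminated by later therapy alongside those cleared by the first ablation.

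TTR has a narrower version of the problem. A lesion coded *Progressing*, or recurrent without enhancement, and then retreated is never an event. That patient runs on as event-free to the last lesion assessment.

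**Working it through.** **1. Search for a rule.** SAP 6.2.1, 6.2.2, 6.4.1–6.4.4, 7.3, 8.6.3, 8.6.4, 8.6.6.1, 8.6.9.1 and 8.8.2 contain no provision that excludes, censors, flags or carries forward as failed an assessment made after later therapy. SAP 7.3 points to 6.4.1 for censoring, but 6.4.1 has none. SAP 6.2.2 lets the sponsor choose one assessment per window by manual review and is silent on retreatment. If failure and rescue fall in one window (for example days 550–915), the post-rescue image may be the one kept.

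**2. Inputs for size.** The documents give about 250 patients and no failure, retreatment or rescue rate, so there is no plan figure to reproduce. Everything below is assumed, with no attrition:

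- f = local failure, 4–12%
- q = share of failures retreated before the visit, 50–90%
- s = rescue success, 80–95%
- u = share of failures never coded recurrent with enhancement, 0–50%

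**3. Per-visit tables.** Failure shown at a later visit = f × (1 − q × s), against f if rescued failures stay counted.

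| f | q=50%, s=80% | q=90%, s=95% | Rescued kept as failures | Gap (points) |
|---|---|---|---|---|
| 4% | 2.4% | 0.6% | 4.0% | 1.6–3.4 |
| 8% | 4.8% | 1.2% | 8.0% | 3.2–6.8 |
| 12% | 7.2% | 1.7% | 12.0% | 4.8–10.3 |

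For example, 0.08 × (1 − 0.9 × 0.95) = 0.0116, or 1.2%.

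**4. TTR.** Freedom from event as planned = 1 − f × (1 − u). If retreatment counted as an event, and all uncoded failures were retreated, it would be 1 − f. At f = 8%:

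- u = 0: 92.0% either way.
- u = 25%: 94.0% against 92.0%.
- u = 50%: 96.0% against 92.0%.

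The gap is f × u. For u of 25–50% it runs from 4% × 25% = 1 point to 12% × 50% = 6 points.

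**5. Lesion size, and why cutting alone fails.** Assume −60% change when controlled or rescued and +20% when failed, with f = 8%, q = 90%, s = 95%.

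- As planned: −60 + 0.0116 × 80 = −59.07%.
- Pre-rescue value kept: −60 + 0.08 × 80 = −53.6%.
- Retreated lesions dropped: (0.92 × −60 + 0.008 × 20) / 0.928 = −59.31%.

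Dropping them makes the mean slightly more favourable, because the dropped lesions are the failures.

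The recurrence table behaves the same way. Suppose 14 of 200 patients recur by month 12 and all are successfully retreated before month 24. The month-24 table shows 0/200. After a cut it shows 0/186. Cumulative recurrence is 14/200 = 7.0%. With a separate category it would show 0 recurrent, 14 (7.0%) retreated and 186 (93.0%) neither.

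**The case against.** The strongest reply is that the registry describes patients under their physicians' standard of care, and Protocol 7.5 includes retreatment in follow-up. All-follow-up summaries are legitimate for that purpose, and the documents do not name durability of a single ablation as the target. This stands as a defence of keeping such tables. It does not defend leaving them unlabelled: the SAP states no all-follow-up strategy, and shrinkage after nephrectomy or other non-cryotherapy treatment is not an outcome of cryotherapy with the sponsor's products.

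The second reply is that retreatment is already disclosed in 8.6.4, 8.8.2 and the patient listings (SAP 7.1). This stands in part, so it would be wrong to say that nothing separates retreated patients. But the 8.6.4 split is ever/never, covers cryoablation only, and does not reach size, waterfall plots or lesion status. SAP 8.8.2 counts therapies without linking them to lesion results.

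Four stronger readings are tempting and are not supported:

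- *TTR as a whole is biased.* A recurrence with enhancement recorded before rescue remains a Kaplan-Meier event unless the missing-baseline or missed-visits rule censors it. The cumulative rates in SAP 8.6.6 therefore already capture those failures.
- *The first-procedure origin is the error.* It suits overall and disease-specific survival, and TTR. The gap is the missing rule for later therapy.
- *The retreated subgroup must show high recurrence.* The table is per visit. After successful rescue, late visits in that subgroup would show low recurrence.
- *The effect is known to be large.* No document gives the rates needed, or shows how a surgically removed lesion is coded.

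Feasibility is a fair caution. Subsequent cryoablation must be found by hand in a free-text therapy field, and no section shows that therapy is linked to a particular lesion.

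**Conclusion.** The gap is real for change in lesion size, the waterfall plots, per-visit recurrence and progression with enhancement, lesion status and the *No longer present* profile. Followed as written, the SAP can show rescued lesions as successes of the first ablation at later visits.

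TTR is affected only in two situations: the failure was not first recorded as *Recurrent* with enhancement, or a censoring rule in 8.6.6.1 removes the event.

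Under the assumed ranges, per-visit failure is understated by 1.6 to 10.3 points. TTR freedom is overstated by 0 points if every failure is coded recurrent with enhancement, and by 1 to 6 points if 25–50% are not. These figures rest entirely on assumed rates; the actual size cannot be obtained from the documents. The matter should be corrected, but it does not undermine the survival analyses.

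**What to change.** Keep the first procedure as time origin and add the following to the SAP, recorded as a change in 5.2:

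1. In the per-visit recurrence and lesion-status tables, keep retreated patients or lesions in the denominator under their own category: retreated or other local therapy since first cryoablation. Do not drop them.
2. Flag lesion-size and waterfall data obtained after later therapy and show them separately, stating the number retreated at each visit.
3. In the *No longer present* profile, exclude or flag lesions that had later therapy.
4. Add a TTR sensitivity analysis counting the first retreatment of a treated lesion as an event. If therapy cannot be linked to a lesion, count any local renal retreatment and say so.
5. Beside the ever/never subgroup, report the share retreated among patients with recurrence.

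SAP 8.8.2 already uses the dates of new local therapy and of retreatment, so no new data collection is evident. The cost is SAP wording and some manual linkage of therapy records to lesions, beyond the manual identification already planned in 8.6.4 and 8.8.2. TTR and lesion-status figures may look less favourable.

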6.2.1.1 Partial Dates

Partial dates are not permitted in the database.

6.2.2 Windows

For the purpose of statistical analysis, visit windows will be calculated as shown below.

Table 2 Analysis Windows for follow-up assessments

Analysis visit name	Visit window (months)	Visit window for analysis (days)
Pre 6 Month	0 to 3	1 to 92
6 Month	3 to 9	93 to 275
12 Month	9 to 18	276 to 549
24 Month	18 to 30	550 to 915
36 Month	30 to 42	916 to 1281
48 Month	42 to 54	1282 to 1647
60 Month	54 to 66	1648 to 2013
Post 60 Month	>66	>2013

Day 1 = date of cryoprocedure

If a patient has more than one assessment occurring in the same visit window, a manual review on a patient-by-patient basis will be performed by Galil Medical to select the analysis visit and will be documented. The assessment to be used will be selected based on completeness of the data and whether or not recurrence is known versus suspected. For example, if imaging at month 13 suggests recurrence and further imaging at month 15 confirms there is/is not recurrence, the confirmatory imaging assessment will be used. If

data between multiple assessments is considered to be similar, the assessment closest to the middle of the visit window will be used.

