5.1. Description of the Registry

TRACE is an observational, open-label, single-arm, multi-center registry of subjects who have undergone renal lesion cryoablation per their physician's standard of care. Patients 18 years of age or older who have been determined to be an appropriate candidate for cryoablation will be offered enrollment into the registry. Subjects will be recruited from a variety of practice settings, including academic centers and community-based physicians. Those agreeing to participate in the registry will read and sign an informed consent form prior to their cryoablation procedure. Subjects will be observed for five years from the date of their cryoablation procedure.

The registry is non-interventional; it will neither direct the cryoablation procedures performed nor define the post-surgery follow-up of each subject. A subject's participation in the registry will not influence or direct subject treatment procedures or follow-up care. Physicians will use their discretion and personal standards of care to select subjects, perform the cryoablation procedures and define appropriate follow-up visit schedules for their subjects; it is anticipated that subjects will be seen at least once per year during the five-year follow-up period of TRACE. Subjects may be followed by the physician performing the cryoablation procedure or by their local/personal physician. The enrolling physician will be responsible for providing the follow-up data to the registry and will, as appropriate, work with a subject's local/personal physician to collect the follow-up data.

A subject's Pre-surgery/Enrollment visit will include the collection of general demographics information, a brief medical history (general and renal specific), comorbidities, diagnosis details (imaging, biopsy) and current classes of medications. Subjects will be asked to complete a pre-surgery quality of life (SF-12) questionnaire. At the cryoablation visit, details of the cryotherapy procedure will be collected, as well as any potentially or directly related adverse events.

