4 STUDY DESIGN

4.1 General Design

This is an observational, open-label, single-arm, multi-center study of patients who have undergone renal lesion cryoablation per their physician's standard of care via a Galil Medical cryoablation system using Galil Medical needles.

Data for patients who agree to participate are collected prospectively. (i.e., registry data collection).

TRACE is anticipated to enroll approximately 250 patients at approximately 10 sites.

Patients will be enrolled from a mix of academic and community-based sites.

The schedule and number of follow-up visits for each patient will be determined by his/her physician's standard of care.

Within this context, semi-annual to annual follow-up during the five-year follow-up period is anticipated though it is recognized that follow-up schedules will vary among enrolled patients. Planned per-patient follow-up is 5 years.

The results generated by the registry database will evaluate the use, safety and effectiveness of cryotherapy for renal lesions and will assess the potential advantages and disadvantages of the procedure (e.g., disease recurrence or progression, disease-specific survival rates, overall survival rates, etc).

It will also provide information on long-term surveillance of patients undergoing renal lesion cryoablation.

In addition, this registry may be used as a continuous quality improvement tool on behalf of the treating physicians and will contribute to the development and refinement of standards of care for treatment and follow-up assessments.

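### In five of the six named analysis windows the sponsor may have to choose by hand, with recurrence status in view, which scan is analysed; a programmed rule should replace this

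*SAP*

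**What the plan says.** SAP 6.2.2 assigns follow-up assessments to windows by day, counting the cryoprocedure as day 1: 6 Month is days 93 to 275, 12 Month 276 to 549, 24 Month 550 to 915, 36 Month 916 to 1281, 48 Month 1282 to 1647 and 60 Month 1648 to 2013. If a window holds several assessments, "a manual review on a patient-by-patient basis will be performed by Galil Medical to select the analysis visit", and the choice is to be documented. The assessment is "selected based on completeness of the data and whether or not recurrence is known versus suspected". The worked example has a suspicious scan at month 13 and a second scan at month 15 that settles the question either way; there, "the confirmatory imaging assessment will be used". If the data are judged similar, "the assessment closest to the middle of the visit window will be used".

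On visit frequency, SAP 4.1 states that "semi-annual to annual follow-up during the five-year follow-up period is anticipated though it is recognized that follow-up schedules will vary", and protocol 5.1 adds that "it is anticipated that subjects will be seen at least once per year". SAP 4.3 states that there is no blinding.

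**The concern.** One hand-picked assessment stands for the patient in each window. It feeds change in lesion size and the waterfall plots (SAP 8.6.3), recurrence and progression with enhancement and the per-visit Fisher tests (8.6.4), lesion status (8.6.9.1) and the post-treatment lesion characteristics (8.8.1). The device maker makes the choice with the images' findings known, and no independent or blinded selector is described.

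The criteria cannot be reproduced by a second person. Completeness and similarity have no definition. The lesion statuses shown in SAP 6.5.1 include no suspected category. The only suspicion variable that the SAP defines is the Hounsfield-unit one, and 6.2.2 does not refer to it.

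The worked example also leaves a case open: a definite recurrence that is retreated and then followed by a clean scan in the same window. Repeat cryoablation is foreseen (SAP 6.2.1 and 8.8.2) and time still runs from the first procedure, so the manual choice decides whether that recurrence appears in the visit's table.

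**Working it through.** **Inputs.** Window limits from SAP 6.2.2; a 6- to 12-month interval from SAP 4.1; 30.4375 days per month from SAP 8.6.6.1; 250 patients from SAP 4.4. Assumption, not in the documents: visit timing varies around its target with an SD of one month (0.5 to 1.5 also tried).

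**The plan's own limits.** The upper limit in days is months × 30.5, rounded up. For 3, 9, 18, 30, 42, 54 and 66 months this gives 92, 275, 549, 915, 1281, 1647 and 2013, which matches the table exactly.

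**Width (upper − lower + 1), against six months = 182.6 days.**

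| Window | Days wide | Relative to 6 months |
|---|---|---|
| 6 Month | 275 − 93 + 1 = 183 | equal |
| 12 Month | 549 − 276 + 1 = 274 | 1.5 times |
| 24 to 60 Month | 915 − 550 + 1 = 366 (same for the others) | 2 times |

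Five of the six named windows are wider than the shorter anticipated interval.

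**Windows with two or more scans, 6-monthly schedule.** Month m falls on day 30.4375m + 1. Scans at months 18, 30, 42 and 54 fall on days 548.9, 914.1, 1279.4 and 1644.6, almost on the window edges at 549, 915, 1281 and 1647. With an SD of 30.4 days and rounding to whole days, the chance that each falls in the earlier window is 0.508, 0.518, 0.528 and 0.538. The scan at the named month is taken as always inside its own window. Then:

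- 12 Month: 0.508 (51%)
- 24 Month: 1 − 0.508 × (1 − 0.518) = 0.755
- 36 Month: 1 − 0.518 × (1 − 0.528) = 0.756
- 48 Month: 1 − 0.528 × (1 − 0.538) = 0.756
- 60 Month: 1 − 0.538 = 0.462 (46%)

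The middle three are about 76%. Simulation agrees, with little change for SDs from 0.5 to 1.5 months: about 51%, 75 to 76%, and 43 to 48% for 60 Month. The 6 Month window stays at 0 to 2%.

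**Regular annual schedule.** One scan per window; the simulated share with two or more is about 0% at every SD tried.

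**Count before dropout.** The sum is 0.508 + 0.755 + 0.756 + 0.756 + 0.462 = 3.237 windows per 6-monthly patient, and 250 × 3.237 ≈ 809 if all patients follow that schedule. If 10%, 25% or 50% do, the count is about 81, 202 or 405.

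**Tie-break at 12 Month.** The middle is (276 + 549)/2 = day 412.5, about month 13.5. A month-12 scan (day 366) is 46.5 days away, so it loses to any scan on days 367 to 458. In a regular 12 and 18 month pair, month 12 still wins (46.5 against 136.5 days). Under 6-monthly scans the midpoint rule and a closest-to-month-12 rule pick different scans in about 0%, 1.6% and 7% of patients at SDs of 0.5, 1 and 1.5 months. The other windows are centred on their named month to within about 0.1 month.

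**The case against.** The strongest reply has four parts.

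- **Neutral rule.** The recurrence criterion concerns certainty, and the worked example uses the confirmatory scan whichever way it turns out. That stands for the example. It does not cover undefined completeness and similarity, or the retreated recurrence described above.
- **Traceability.** Choices are documented, and SAP 7.1 promises listings of all eCRF data, so unselected scans stay visible. That also stands, but a traceable choice is not a prespecified one.
- **Limited reach.** Overall and disease-specific survival (8.6.6.2 and 8.6.6.3) do not use selected scans. Time to recurrence (6.4.4 and 8.6.6.1) runs to a recurrence date, and nothing restricts it to selected assessments. The exposed outputs are mainly descriptive, in a registry without a power calculation. This is correct and bounds the point.
- **Unknown frequency.** Follow-up is semi-annual to annual, and annual scanning leaves nothing to choose. This is correct for regular schedules. Extra scans are not random, however: the SAP's own month 13 and 15 example is a work-up of suspected recurrence, so even under annual follow-up the choices would fall on the patients who determine the recurrence percentages.

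A reader might infer three stronger things that the documents do not support. One is that the 12 Month results drift toward month 14: under 6-monthly scans with an SD of about one month, the midpoint rule picks month 12.1 on average, and it applies only to similar data. Another is that 800 manual choices will occur: that figure needs every patient on 6-monthly scans for five years without dropout, and it includes windows that the midpoint rule settles. The third is that lesions will look smaller because the smaller reading is taken: size is not a selection criterion in 6.2.2, so that would be a departure from the SAP.

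**Conclusion.** The concern holds for the by-visit lesion outputs. The SAP prescribes unblinded, case-by-case selection by the sponsor on undefined criteria, one of which is recurrence status, in windows wide enough for several scans.

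The number of affected windows lies between near 0 (all regular annual) and about 800 (all 6-monthly, 250 patients, no dropout), plus work-up scans. The documents give neither the schedule mix nor scan counts, so no single figure can be defended. The direction and size of any bias cannot be derived from the documents either. The off-centre 12 Month tie-break is a minor, separate defect.

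**What to change.** Replace the manual review in SAP 6.2.2 with a programmed rule applied to all patients:

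- **Size:** use the non-missing investigator-read assessment closest to the named month's target day, with the earlier one on ties. With the procedure as day 1, the targets are 30.4375 × months + 1, that is days 184, 366, 732, 1097, 1462 and 1827 after rounding. This also removes the 12 Month tie-break problem.
- **Recurrence or progression:** count the window positive if any assessment in it is recorded as positive, unless a later confirmatory assessment, made before any further therapy, is recorded as negative.
- **Fisher comparison with Hounsfield-unit suspicion (8.6.4):** take both variables from the same assessment, so that results from different scans are not paired.
- **Manual selection:** report the documented choices only as a sensitivity analysis.

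The cost is SAP wording and programming, and no data are lost. The price is that some by-visit recurrence percentages may be slightly higher, and that size and recurrence within one window may come from different scans. The table footnotes should say so.
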